13.4 Local Tolerability Assessments

The investigator's dermal response assessment of the application site reaction (0= no evidence of irritation to 7= strong reaction spreading beyond application site) will be summarized by visit and

 Innovaderm Research	STATISTICAL ANALYSIS PLAN, Final Version 1.0
Protocol Number: ARQ-151-313	Sponsor: Arcutis Biotherapeutics, Inc.

treatment group as defined in Section 5 using both categorical methods (number and percentage of subject with each score) as well as continuous methods (descriptive statistics).

The investigator's assessment of the application site reaction other effects (slight glazed appearance, marked glazing, glazing with peeling and cracking, glazing with fissures, film of dried serous exudates, small petechial erosions and/or scabs, and no other effects) will be summarized using number and percentage of subjects in each category by visit and treatment group as defined in Section 5.

Local tolerability (burning/stinging scored as 0= none to 3= severe) as assessed by the subject (parents/guardian for subjects < 6 years of age) will be summarized similarly.

13.5 Patient Health Questionnaire Depression Scale (PHQ-8) and Patient Health Questionnaire Depression Scale (Modified PHQ-A)

The PHQ-8 assessment will be performed in adult subjects (≥ 18 years of age) while the modified PHQ-A assessment (question 9 has been removed since it is better evaluated by use of the C-SSRS tool) will be performed in adolescent subjects (12-17 years of age).

The PHQ-8/Modified PHQ-A score is the sum of the responses for the 8 questions, each question ranging from 0 (Not at all) to 3 (Nearly every day). The score will be computed as defined in Section 5.5.

Then, five severity categories of depression are defined based on the PHQ-8/Modified PHQ-A score as follows:

- None – Minimal depression (0 to 4)
- Mild depression (5 to 9)
- Moderate depression (10 to 14)
- Moderately severe depression (15 to 19)
- Severe depression (20 to 24)

The number and percentage of subjects in each category of depression will be summarized by visit and treatment group as defined in Section 5.

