Descriptive statistics will be calculated for quantitative safety data and frequency counts will be compiled for classification of qualitative safety data.

The subject incidence of treatment-emergent adverse events (TEAE) will be summarized overall, by severity, and by attribution.

Statistical Methods:

Descriptive statistics will be presented for the endpoints and safety data collected in the clinical trial. This includes the number and percentage of subjects for binary endpoints/categorical data, and mean, SD, median, Q1, Q3, minimum, and maximum for continuous data.

Adverse Events

For the primary endpoints, the occurrence of TEAEs and the occurrence of Serious Adverse Events (SAEs) will be tabulated by preferred term and system organ class.

In addition, summary tables of TEAEs by severity, by relationship to investigational product, and those leading to withdrawal from investigational product will be created.

Vital Signs

Descriptive statistics will be calculated for vital signs over time.

Clinical Laboratory Results

Descriptive statistics of the laboratory parameters will be calculated at each scheduled time point. Shifts from baseline will be tabulated.

[figure not shown]
Patient Health Questionnaires

CDI-2 (in 6-11 year-olds), PHQ-8 (in adults), a modified version of the PHQ-A (in adolescents), and C-SSRS questionnaires (in adolescents and adults) will be completed at all study visits. Descriptive statistics will be calculated for the CDI-2, PHQ-8, and Modified PHQ-A. The C-SSRS will be analyzed per the Scoring and Data Analysis Guide from the Columbia Lighthouse Project.

Efficacy Assessments

Descriptive statistics will be presented for the efficacy data collected in the clinical trial for the subjects who enroll in this study and receive at least one day of study drug. For the binary and continuous endpoints related to vIGA-AD, WI-NRS, and EASI, descriptive statistics will be provided for the endpoints each scheduled visit.

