5.1.7. Patient Health Questionnaire Depression Scale (PHQ-8)

The PHQ-8 Assessment ([Appendix 1](#)) will be performed in adult subjects according to the Schedule of Visits and Assessments ([Section 1.3](#)).

PHQ-8 score is the sum of the responses for the 8 questions.

Five severity categories of depression are defined as follows:

- None – Minimal depression (0 to 4)
- Mild depression (5 to 9)
- Moderate depression (10 to 14)
- Moderately severe depression (15 to 19)
- Severe depression (20 to 24)

A subject with a PHQ-8 score of 10-14 should be referred to a mental health professional for evaluation, regardless of the reason for their change in score.

A subject with a PHQ-8 score ≥ 15 should be immediately referred to a mental health professional, and Investigators in consultation with the mental health professional should consider interruption or discontinuation of the study drug.

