2 STUDY OBJECTIVES AND ENDPOINTS

OBJECTIVES	ENDPOINTS
Safety	
To assess long-term safety in subjects with atopic dermatitis (AD) treated with Roflumilast cream 0.15%	Primary safety endpoints: 
 • Treatment-emergent Adverse Events (TEAEs) • Serious Adverse Events (SAEs)

Protocol Number: ARQ-151-313

Sponsor: Arcutis Biotherapeutics, Inc.

OBJECTIVES	ENDPOINTS

once daily (QD; subjects \geq6 years of age) or Roflumilast cream 0.05% QD (subjects 2 to 5 years of age) after completing one of three Phase 3 studies (ARQ-151-311 or ARQ-151-312 or ARQ-151-315).
	
Other safety endpoints:
 
 Changes and percent change in clinical laboratory results Changes and percent change in vital signs Local tolerability assessments Change from baseline of Patient Health Questionnaire depression scale (PHQ-8) and Modified PHQ-9 for Adolescents (PHQ-A) total score Change from baseline of Children's Depression Inventory 2nd Edition (CDI-2) total score Columbia-Suicide Severity Rating Scale (C-SSRS)

Efficacy
 
To evaluate the long-term efficacy in subjects with AD treated with roflumilast cream 0.15% QD (subjects \geq6 years of age) or roflumilast cream 0.05% QD (subjects 2 to 5 years of age) after completing one of three Phase 3 studies (ARQ-151-311 or ARQ-151-312 or ARQ-151-315).
	
Secondary efficacy endpoints:
 
 Validated Investigator Global Assessment-Atopic Dermatitis (vIGA-AD) score of clear (0) or almost clear (1) at each assessment vIGA-AD success (defined as vIGA-AD score of clear (0) or almost clear (1) plus at least a 2-grade improvement from baseline) at each assessment In subjects \geq 12 years old at the start of the parent study, change and percent change from baseline in Worst Itch - Numeric Rating Score (WI-NRS) over time ^a Change and percent change from baseline in Eczema Area and Severity Index (EASI) total score over time 
Other efficacy endpoints:
 
 Duration of the first twice weekly (BIW) dosing interval Cumulative time (days) on BIW dosing

Protocol Number: ARQ-151-313

Sponsor: Arcutis Biotherapeutics, Inc.

OBJECTIVES	ENDPOINTS

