5.2 Baseline

There are two baseline definitions for the analyses:

- Primary baseline is defined as the last observation before or on the first dose of roflumilast cream 0.15% or 0.05% in ARQ-151 parent studies for subjects administered roflumilast previously and before or on the first dose of roflumilast cream 0.15% or 0.05% in this study* for subjects administered vehicle previously.
- OLE baseline is defined as the last observation before or on the first dose of roflumilast cream 0.15% or 0.05%* in this study.

If the last non-missing assessment was performed on the same date as the first dose of roflumilast cream* and time is not available, the assessment will be considered as baseline, except for adverse events (AEs) and medications starting on the first dose date which will be considered post-baseline. For subject local tolerability assessments, if the last non-missing assessment was performed on the same date as the first dose of roflumilast cream*, the assessment will be considered as baseline, regardless of the time of the assessment.

For the subjects administered vehicle in the parent study, the definition for Primary and OLE baselines are the same.

* Enrollment date (usually the Week 4 visit in the parent study) for enrolled subjects who discontinued early from this study before the first application of roflumilast cream 0.15% or 0.05%.

The following table ([Table 2](#)) described the baseline used in the analysis:

 Innovaderm Research	STATISTICAL ANALYSIS PLAN, Final Version 1.0
Protocol Number: ARQ-151-313	Sponsor: Arcutis Biotherapeutics, Inc.

Table 2 Summary of Primary/OLE Baseline in the Analyses

Analyses	Baseline*
Demographics and Baseline Characteristics	Primary baseline and OLE baseline, as applicable
Efficacy Analysis	Primary baseline and OLE baseline
Safety analysis for AEs and concomitant medications	OLE baseline
Safety analysis for clinical laboratory, vital signs, local tolerability assessments. PHQ-8, Modified PHQ-A, CDI-2, C-SSRS, and physical examination	Primary baseline

* Refer to Section 8 for more details.

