- IDQOL Total Score = sum of the 10 questions (individual question 1 scored as All the time= 3, A lot= 2, A little= 1, None= 0; individual question 2 scored as: Always crying, extremely difficult= 3, Very fretful= 2, Slightly fretful= 1, Happy= 0; individual question 3 scored as More than 2 hours= 3, 1 – 2 hours= 2, 15 minutes – 1 hour= 1, 0 – 15 minutes= 0; individual question 4 scored as 5 hours or more= 3, 3 – 4 hours= 2, 1 – 2 hours= 1, Less than 1 hour= 0; individual questions 5 to 10 scores as Very much= 3, A lot= 2, A little= 1, Not at all/None= 0), ranging from 0 to 30. If 1 item is missing, that item is scored as 0. If 2 or more items are missing, the score should not be calculated. Of note, the severity of eczema question is scored and reported separately than the IDQOL total score. The IDQOL

 Innovaderm Research ■■■	STATISTICAL ANALYSIS PLAN, Final Version 1.0
Protocol Number: ARQ-151-313	Sponsor: Arcutis Biotherapeutics, Inc.

will be completed by parents/caregivers for subjects with age < 4 years based on age at start of the preceding study ARQ-151-315.

- DFI Total Score = sum of the 10 questions (individual questions scored as Very much=3, A lot=2, A little=1; Not at all=0) ranging from 0 to 30. If 1 item is missing, it is scored as 0 for that item. If 2 or more items are missing, the score should not be calculated. The DFI will be completed by parents/caregivers for all subjects \geq 2 years of age and \leq 17 years of age. Please note that the DFI is not to be conducted for subjects who were \leq 17 years of age in the ARQ-151-311/312 studies and turned 18 years of age prior to enrollment into ARQ-151-313.
- PHQ-8 Total Score = sum of the 8 questions (individual questions scored as Not at all=0, Several days=1, More than half the days=2, and Nearly every day=3), ranging from 0 to 24. If more than 1 item is missing the score should not be calculated. If 1 item is missing the score is calculated as (sum of answered items*8)/number of answered items (i.e., 7). The PHQ-8 Assessment will be performed in adult subjects based on age at start of preceding studies ARQ-151-311/312.

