13.2 Clinical Laboratory

For continuous hematology, chemistry, and urinalysis tests, observed values, changes from primary baseline, and percent changes from primary baseline will be summarized descriptively by visit and treatment group as defined in Section 5. Categorical urinalysis tests will be summarized using frequencies by visit and treatment group. Of note, hematology, chemistry, and urinalysis tests will only be collected in subjects ≥ 12 years of age at time of enrollment in the parent study.

Shift tables from primary baseline to each post-baseline visit describing shifts to out-of-normal range will be provided for chemistry, hematology, quantitative and qualitative urinalysis tests. Only subjects with a baseline result and a result at the specified post-baseline visit for the test will be considered.

Listings of abnormal laboratory will be provided for each test where a subject had at least one abnormal result.

Laboratory data will be presented in SI units.

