13.6 Children's Depression Inventory 2 (CDI-2)

The CDI-2 assessment will be performed in children subjects (6-11 years old, inclusive).

The observed values and changes from both primary and OLE baseline will be calculated for CDI-2 total score and the 2 subscales (refer to Section 5.5), and will be summarized descriptively by visit and previous treatment group in parent studies as defined in Section 5.

 Innovaderm Research	STATISTICAL ANALYSIS PLAN, Final Version 1.0
Protocol Number: ARQ-151-313	Sponsor: Arcutis Biotherapeutics, Inc.

A CDI-2 total score ≥ 21 for females and ≥ 22 for males is considered as meeting clinically significant depression. The proportion of subjects meeting the clinically significant criteria will also be summarized by visit and previous treatment group in parent studies as defined in Section 5.

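### SAP 13.5 plans only severity-category counts by visit for PHQ-8 and PHQ-A, so no specified table shows within-subject worsening, although change from baseline is a listed endpoint

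*SAP*

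**What the plan says.** **Endpoint and baseline.** SAP Section 2 lists among the other safety endpoints: "Change from baseline of Patient Health Questionnaire depression scale (PHQ-8) and Modified PHQ-9 for Adolescents (PHQ-A) total score". SAP 5.2 Table 2 assigns the Primary baseline to the row reading "Safety analysis for clinical laboratory, vital signs, local tolerability assessments. PHQ-8, Modified PHQ-A, CDI-2, C-SSRS, and physical examination". SAP 5.5 defines both total scores and a general change-from-baseline formula.

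**Planned PHQ output.** SAP 13.5 sets out five integer severity bands (0–4, 5–9, 10–14, 15–19, 20–24) and one summary: "The number and percentage of subjects in each category of depression will be summarized by visit and treatment group as defined in Section 5".

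**Neighbouring sections.** For CDI-2, SAP 13.6 says: "The observed values and changes from both primary and OLE baseline will be calculated for CDI-2 total score and the 2 subscales". For laboratory data, SAP 13.2 says: "Shift tables from primary baseline to each post-baseline visit describing shifts to out-of-normal range will be provided for chemistry", with hematology and urinalysis also covered.

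**Protocol.** The synopsis promises: "Descriptive statistics will be calculated for the CDI-2, PHQ-8, and Modified PHQ-A". At a PHQ-8 score of 15 or more, Protocol 5.1.7 says that investigators, with a mental health professional, "should consider interruption or discontinuation of the study drug". A score of 10–14 leads to referral. Protocol 5.1.8 says the same for the modified PHQ-A.

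**Data handling.** SAP 5.4 uses unscheduled and early-termination (ET) values in by-visit summaries only where there is no scheduled value and the measurement falls within the visit window. It also says that all such measurements will be listed. SAP 8 summarises PHQ-8 and PHQ-A at Primary Baseline. For missing items, SAP 5.5 says: "If 1 item is missing the score is calculated as (sum of answered items*8)/number of answered items (i.e., 7".

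**The concern.** The PHQ endpoint is defined as a change, but the only output in its analysis section is cross-sectional. Nothing in SAP 13.5 uses the baseline that Table 2 assigns. Because 13.2, 13.3 and 13.6 each spell out change from baseline, the silence in 13.5 looks like an omission. The legible text of SAP 3.6 records no decision to drop it.

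Long-term safety is the primary objective, and Protocol 2.3.2 reports psychiatric adverse events in 5.9% of patients on oral roflumilast against 3.3% on placebo, with depression among the most common. For adults and adolescents the PHQ is the study's systematic depression measure. A table that cannot distinguish a subject who entered with moderate symptoms from one who developed them on treatment does not answer the safety question. SAP 6.3 runs all planned analyses at the interim, so the gap would carry into that report as well.

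**Working it through.** No sample size, power or alpha figure is involved (SAP 5.7 plans no hypothesis tests), and the plan gives no figure to reproduce beyond the score range, 8 items × 3 = 24, which is correct.

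**1. What each measure gets after baseline, as specified in its own section**

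| Measure | Observed values | Change from baseline | Shift table | Category or threshold counts |
|---|---|---|---|---|
| Laboratory (13.2) | yes | yes | yes | – |
| Vital signs (13.3) | yes | yes | no | weight change >5% |
| CDI-2 (13.6) | yes | yes | no | clinically significant score |
| PHQ-8/PHQ-A (13.5) | not specified | not specified | no | five bands |

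**2. What by-visit counts can say about new cases.** Let N subjects be assessed at both times, with b at 10 or more at baseline and v at 10 or more at a visit. The number of new cases lies between max(0, v − b) and min(v, N − b). The documents give no counts, so these are assumed:

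- N = 100, b = 5, v = 5: 0 to 5 new cases
- N = 100, b = 10, v = 8: 0 to 8
- N = 100, b = 2, v = 5: 3 to 5

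The counts do not identify new onset; a shift table does. Baseline cases are possible: Protocol 4.5.2 excludes a history of severe depression but states no PHQ limit.

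**3. Scores left out of the by-visit table.** Inputs are the target days and window ends in SAP 5.4 Table 3. If each scheduled visit falls on its target day, an ET or unscheduled score taken afterwards but still inside that window is not used.

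| Visit | Target day | Window ends | Days after the visit, same window | Days between this visit and the next |
|---|---|---|---|---|
| Week 4 | 29 | 57 | 28 | 55 |
| Week 12 | 85 | 127 | 42 | 83 |
| Week 24 | 169 | 211 | 42 | 83 |
| Week 36 | 253 | 309 | 56 | 111 |
| Total | | | 168 | 332 |

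168/332 = 51%. For Cohort-Week 24 the first two rows apply: (28 + 42)/(55 + 83) = 70/138 = 51%. This is a share of calendar days, not of cases. It matters mainly for ET visits, where the Week 52 procedures, including the PHQ, are done (Protocol 5.5). Protocol 5.6 does not list the PHQ among routine unscheduled assessments.

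**4. Prorated totals.** With exactly one item missing, total = s × 8/7, where s is the sum of seven items and can take 22 values (0 to 21). Four of them fall between bands:

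- s = 4: 4.57, between 0–4 and 5–9
- s = 8: 9.14, between 5–9 and 10–14
- s = 13: 14.86, between 10–14 and 15–19
- s = 17: 19.43, between 15–19 and 20–24

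The other 18 sums land inside a band. SAP 5.5 and 13.5 state no rounding rule for these totals.

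**The case against.** **The general provisions already cover it.** SAP 5.6 says that all continuous variables will be summarised, by visit where applicable. Baseline, score and change formula are all defined, the protocol promises descriptive statistics, and table shells sit in a separate document. This stands in part. A reader might infer from 13.5 that the endpoint will never be analysed, but the documents support only that no such output is specified there.

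**The data will be visible.** All scores are listed and baseline PHQ is summarised, so new and pre-existing cases can be separated subject by subject. That is true, but in a study of up to about 1,500 subjects a listing does not replace a summary.

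**Change from baseline would not itself show emergence.** Correct: a mean change can dilute a few marked worsenings. Adding it completes the listed endpoint; the shift table is what shows emergence. Neither document commits to a worst-value PHQ table, and CDI-2 has none, so that part is a recommendation and not an unmet commitment.

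**Stopping at 15 or more.** A reader might infer that the stopping provision removes affected subjects before they can be counted, so that the table looks flat while cases accumulate. The documents do not support this. The decision is discretionary and concerns study drug (Protocol 4.7.5); PHQ is not among the reasons for removal from the study (4.7.6). A case found at a scheduled visit is counted at that visit. If every such subject then left, the visit counts would simply add up to the cumulative number.

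**Other capture.** Depression reported as an adverse event, discontinuations and C-SSRS results are tabulated (SAP 13.1, 7.1, 13.7). This limits the consequence but does not summarise the PHQ data.

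**Conclusion.** The point holds as a gap in specification. A listed safety endpoint with an assigned baseline has no output in its analysis section, and the one planned table cannot separate new from pre-existing depression. It also omits some ET and unscheduled scores. This should be corrected, but it does not threaten the primary endpoints (TEAEs and SAEs), and the data needed are already collected and listed.

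The size of any distortion cannot be estimated from the documents. The ranges of new cases rest on assumed counts, and the 51% assumes scheduled visits on their target days. The prorating gap is real but small: 4 of 22 possible sums, and only when exactly one item is missing.

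**What to change.** In SAP 13.5:

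- **(a)** Add observed PHQ-8 and PHQ-A total score and change from Primary Baseline by visit and treatment group, in the manner of 13.6.
- **(b)** Add a shift table from Primary Baseline category to worst post-baseline category, using all scheduled, unscheduled and ET assessments in this study. The denominator is subjects with a baseline and at least one post-baseline score. Report alongside it the number of subjects ever reaching 10 or more and 15 or more, the levels at which the protocol already calls for action.
- **(c)** State that prorated totals are rounded to the nearest integer before they are placed in a category. The four gap values then become 5, 9, 15 and 19. The rule is for analysis categories only and has no bearing on clinical referral or treatment decisions.

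The cost is SAP wording and two or three descriptive tables. No new data are needed, and there is no effect on sample size or error rates.

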13.6 Children's Depression Inventory 2 (CDI-2)

The CDI-2 assessment will be performed in children subjects (6-11 years old, inclusive).

The observed values and changes from both primary and OLE baseline will be calculated for CDI-2 total score and the 2 subscales (refer to Section 5.5), and will be summarized descriptively by visit and previous treatment group in parent studies as defined in Section 5.

 Innovaderm Research	STATISTICAL ANALYSIS PLAN, Final Version 1.0
Protocol Number: ARQ-151-313	Sponsor: Arcutis Biotherapeutics, Inc.

A CDI-2 total score ≥ 21 for females and ≥ 22 for males is considered as meeting clinically significant depression. The proportion of subjects meeting the clinically significant criteria will also be summarized by visit and previous treatment group in parent studies as defined in Section 5.

13.7 Columbia-Suicide Severity Rating Scale (C-SSRS)

The C-SSRS questionnaire prospectively assesses Suicidal Ideation and Suicidal Behavior and will be performed for subjects 12 years of age and older. The “Since Last Visit” version will be used at all visits. The C-SSRS will be analyzed as per the Scoring and Data Analysis Guide from the Columbia Lighthouse Project (<https://cssrs.columbia.edu/wp-content/uploads/ScoringandDataAnalysisGuide-for-Clinical-Trials-1.pdf>).

Tables will include results from the Suicidal Ideation and Suicidal Behavior sections of the C-SSRS. Frequencies and percentages of subjects with a response of “Yes” at any point on the Suicidal Ideation and Suicidal Behavior items will be summarized by study visit and treatment group as defined in Section 5.

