1.3. Schedule of Visits and Assessments

Study Procedure	Day 1	Wk 4	Wk 12	Wk18	Wk 24 ^t	Wk 30	Wk 36	Wk 44	Wk 52/ET
Visit #	1(Week 4) of ARQ-151-311 or ARQ-151-312 or ARQ-151-315	2	3	Phone Visit	4	Phone Visit	5	Phone Visit	6
Visit Window		+/- 3 days	+/- 7 days	+/- 7 days	+/- 7 days	+/- 7 days	+/- 7 days	+/- 7 days	+/- 7 days
Informed consent/assent	X								
Physical examination ^a	X ^s	X			X				X
I/E criteria	X								
Hematology, Serum Chemistries, and Urine Analysis ^b	X ^s				X				X
Vital signs, height, weight ^c	X ^s	X	X		X		X		X
vIGA-AD, EASI, BSA, SCORAD ^d	X ^s	X	X		X		X		X
WI-NRS pruritus ^e	X ^s								
POEM ^f	X ^s	X	X		X		X		X
Local Tolerability Assessment ^g	X	X	X		X		X		X
CDI-2, PHQ-8, PHQ-A, C-SSRS ^h	X ^s	X	X		X		X		X
DLQI, CDLQI, IDQOL, DFI ⁱ	X ^s	X	X		X		X		X
Medical Photography ^j	X ^s	X	X		X		X		X
Urine pregnancy test ^k	X ^s	X	X		X		X		X
PK draws ^l									X

Study Procedure	Day 1	Wk 4	Wk 12	Wk18	Wk 24 ^t	Wk 30	Wk 36	Wk 44	Wk 52/ET
Visit #	1(Week 4) of ARQ-151-311 or ARQ-151-312 or ARQ-151-315	2	3	Phone Visit	4	Phone Visit	5	Phone Visit	6
Visit Window		+/- 3 days	+/- 7 days	+/- 7 days	+/- 7 days	+/- 7 days	+/- 7 days	+/- 7 days	+/- 7 days
Dispense study medication kit ^m	X	X	X		X		X		
Drug application and Parents/Caregivers training in clinic	X								
Dispense/review diary ⁿ	X	X	X		X		X		X
Maintenance Dosing Determination ^o		X	X		X		X		
Weigh study medication ^p	X	X	X		X		X		X
Compliance Determination ^q		X	X		X		X		X
Adverse event assessment ^r	X	X	X	X	X	X	X	X	X
Concomitant medications	X	X	X	X	X	X	X	X	X
Study Exit					X ^t				X

^a Limited physical examination: skin, lungs, and heart only

^b Hematology, Serum Chemistries, and Urine Analysis will only be done in subjects \geq 12 years of age at time of enrollment in the preceding study.

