4.3. Subject Participation

Subject participation involves a minimum of five clinic visits at Week 4, Week 12, Week 24, Week 36 and Week 52 of treatment. There will be three phone visits conducted at Weeks 18, 30 and 44. (For Cohort-Week 24, subject participation involves a minimum of three clinic visits at Week 4, Week 12 and Week 24 of treatment. There will be one phone visit conducted at Week 18). The Day 1 visit of this study will be Week 4 of the ARQ-151-311 or ARQ-151-312 or ARQ-151-315 study. The baseline value for safety and efficacy will be the last observation prior to the first dose of ARQ-151 cream in either the ARQ-151 preceding study (ARQ-151-311 or ARQ-151-312 or ARQ-151-315), or this study. The anticipated maximum duration of subject participation is about 24 or 52 weeks. Subjects in the ARQ-151-311 or ARQ-151-312 or ARQ-151-315 study that choose to participate in the long-term extension study will transition directly into the ARQ-151-313 study at the Day 1 visit (Week 4 of Study ARQ-151-311 or ARQ-151-312 or ARQ-151-315).

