5.1.10. Columbia-Suicide Severity Rating Scale (C-SSRS)

C-SSRS Assessments will be performed according to the Schedule of Visits and Assessments ([Section 1.3](#)) for subjects 12-years old and older.

The administration schedule of the C-SSRS will be:

- The “Since Last Visit” version ([Appendix 4](#)) will be used at all visits.
- A score greater than 0 at the Baseline visit in suicidal ideation may indicate the need for mental health intervention. The investigator should not enroll the subject in the study.
- Any score greater than 0 in the suicidal ideation score may indicate the need for mental health intervention. The Investigator should give consideration for the subject to discontinue from the study drug and prompt referral to an identified mental health professional and/or an appropriate emergency room. The Medical Monitor should be contacted.

The C-SSRS administer will be trained via the C-SSRS training video. A training certificate for the administer(s) will be on file in the trial master file at the study site.

The Investigator must review the completed C-SSRS. A qualified mental health care provider must be available, immediately if needed, to refer the subject for further evaluation.

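### C-SSRS percentages by visit rest on look-backs of 4 to 16 weeks, so they are not comparable over time, and SAP 13.7 specifies no clear whole-study summary to set beside them

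*SAP*

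**What the plan says.** Protocol 5.1.10 says that the 'Since Last Visit' form of the C-SSRS "will be used at all visits", and SAP 13.7 repeats this. Neither says whether a telephone contact counts as the last visit.

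In the Protocol 1.3 schedule, the row "CDI-2, PHQ-8, PHQ-A, C-SSRS" is marked at Day 1 and at Weeks 4, 12, 24, 36 and 52/ET, and is blank at the telephone contacts. Protocol 4.3 gives the same pattern: "Subject participation involves a minimum of five clinic visits at Week 4, Week 12, Week 24, Week 36 and Week 52 of treatment"; "For Cohort-Week 24, subject participation involves a minimum of three clinic visits at Week 4, Week 12 and Week 24 of treatment"; and "There will be three phone visits conducted at Weeks 18, 30 and 44". Protocol 5.1.13 limits the calls to adverse events and concomitant medication.

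For the analysis, SAP 13.7 says that Yes responses on the ideation and behaviour "items will be summarized by study visit and treatment group as defined in Section 5". It also refers to an external Columbia scoring and analysis guide. Exposure-adjusted incidence rates (EAIRs) are specified for the adverse event tables (SAP 5.6 and 13.1), and SAP 13 rules out confidence intervals for safety endpoints other than EAIRs.

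Under SAP 5.4, an early-termination (ET), unscheduled or retest value enters a by-visit summary only when no scheduled value is available and the value falls in the analysis window. Otherwise it is only listed. Protocol 5.5 asks for the Week 52 procedures at ET, which include the C-SSRS.

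**The concern.** Each answer reports whether something happened since the previous assessment, so each by-visit percentage is an incidence over that interval. The intervals lengthen as the study goes on, but the table sets the percentages side by side with no adjustment.

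Protocol 2.3.2 describes suicidal ideation and completed suicide in patients taking oral roflumilast. SAP 13.5 says that item 9 was dropped from the adolescent depression scale because the C-SSRS covers it better. The primary objective is long-term safety in a single-arm study, so a reader will naturally look at how suicidality changes with time on drug. The planned table can make a steady rate look like a rise, and can hide a real fall. It can also leave out a Yes recorded as a subject leaves the study.

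**Working it through.** **Inputs.** C-SSRS target days come from SAP 5.4, Table 3: 29, 85, 169, 253 and 365, with Day 1 as the start. As a check, 7 × week + 1 for Weeks 4, 12, 24, 36 and 52 reproduces these days exactly. The documents give no C-SSRS event rate, so there is no planned figure to reproduce. The rate is an assumption, taken over a range.

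**Look-back.** Differences between successive target days: 28, 56, 84, 84 and 112 days, or 4, 8, 12, 12 and 16 weeks. Week 52 to Week 4 is 112/28 = 4. For Cohort-Week 24 the maximum is 84/28 = 3.

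**Expected percentage at a constant rate.** For new, independent events with assumed 4-week probability p, the expected percentage is 100 × [1 − (1 − p)^(look-back days/28)].

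| Assumed p | Wk 4 | Wk 12 | Wk 24 | Wk 36 | Wk 52 | Wk 52/Wk 4 | Wk 24/Wk 4 |
|---|---|---|---|---|---|---|---|
| 0.1% | 0.10 | 0.20 | 0.30 | 0.30 | 0.40 | 3.99 | 3.00 |
| 0.5% | 0.50 | 1.00 | 1.49 | 1.49 | 1.99 | 3.97 | 2.99 |
| 1% | 1.00 | 1.99 | 2.97 | 2.97 | 3.94 | 3.94 | 2.97 |
| 5% | 5.00 | 9.75 | 14.26 | 14.26 | 18.55 | 3.71 | 2.85 |
| 10% | 10.00 | 19.00 | 27.10 | 27.10 | 34.39 | 3.44 | 2.71 |

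Four-fold is the rare-event limit. The rise is stepwise and flat from Week 24 to Week 36.

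**A hidden fall.** If the hazard dropped by 25% after Week 36, Week 52 would carry 16 × 0.75 = 12 weeks' worth of events, the same as Week 36. The two columns would look equal.

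**Persistent ideation.** Take p = 1% and let a share c of the positives be persistent, so that they answer Yes at every visit. The percentage is then c·p + 1 − [1 − (1 − c)p]^(look-back days/28). The Week 52/Week 4 ratio is 3.94 for c = 0, 3.22 for c = 0.25, 2.49 for c = 0.5, 1.75 for c = 0.75 and 1 for c = 1.

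**Visit windows.** With ±3 days at Week 4 and ±7 days later, the look-back ratio runs from (112 − 14)/(28 + 3) = 3.2 to (112 + 14)/(28 − 3) = 5.0.

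**Counting telephone contacts as visits.** Look-backs become 4, 8, 6, 6 and 8 weeks, at most 2-fold. They sum to 32, so 52 − 32 = 20 weeks would never be asked about.

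**The SAP 5.4 rule.** Suppose the Week 24 visit is on Day 169 and the subject leaves with a Yes at ET on Day 190. Both days fall in the Week 24 window (128 to 211), so the scheduled value is used and the Yes appears only in a listing. Window width also mixes look-backs within one column, because Week 52 takes any day from 310. An ET on Day 310 after an on-target Week 36 visit looks back 310 − 253 = 57 days. A Week 52 visit after a missed Week 36 visit looks back 365 − 169 = 196 days.

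**The case against.** A reader might infer that this table will show suicidality rising 4-fold. The documents do not support that. The figure needs new, independent events at a constant rate, counts clinic visits only, and applies only to Cohort-Week 52. Ideation can persist, which pulls the ratio towards 1. Subjects with a history of suicidal ideation are excluded (Protocol 4.5.2), and ideation is a listed reason for stopping treatment (Protocol 4.7.5). Either could change the rate or the set at risk over time. These qualifications stand: 4-fold is a ceiling, not a forecast.

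A reader might also infer that the SAP rules out a cumulative summary. It does not quite do so. SAP 13.7 counts a Yes at any point and defers to an external guide that cannot be checked here. But the same sentence ends with a by-visit breakdown, and no whole-period table is described. The doubt is a reason to settle the point in the SAP text.

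Nor do the documents support two further readings. One is that comparisons between parent-treatment groups are distorted: at the same visit they share the same nominal look-back. The other is that Day 1 has a known, shorter look-back: the parent-study C-SSRS schedule is not provided.

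Finally, counts will be small and are shown alongside the percentages. With an illustrative 400 subjects at both visits and p = 0.5%, the expected numbers are 400 × 0.005 = 2.0 at Week 4 and 400 × 0.01985 = 7.9 at Week 52; at p = 0.1% they are 0.4 and 1.6. Psychiatric TEAEs with EAIRs, and the depression scales with their fixed two-week recall, give other cover. This limits the harm. It does not make the C-SSRS columns comparable.

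**Conclusion.** The concern holds as a matter of comparability over time. On target days, the by-visit percentages cover 4, 8, 12, 12 and 16 weeks without adjustment. The resulting distortion is at most about 4-fold at Week 52 and 3-fold at Week 24 for new, independent events at a constant rate, and falls to none if all ideation is persistent. These bounds take 'last visit' to mean the previous clinic C-SSRS. That is the natural reading of the schedule, but it is not stated. The loss of an ET or unscheduled Yes from the by-visit table follows directly from SAP 5.4. It matters mainly for ET, because Protocol 5.6 does not list the C-SSRS among unscheduled-visit assessments. The change is worth making before the analyses are run.

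**What to change.** In SAP 13.7:

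- Make the main C-SSRS display the number and percentage of subjects with any post-Day 1 Yes over the whole extension, with ideation and behaviour separate, and with ET and unscheduled assessments included. Take as denominator the subjects who are given the C-SSRS (12 years and over).
- Add an exposure-adjusted rate per 100 patient-years with a 95% CI, counting subjects as in the SAP 5.5 definition. SAP 13 already allows confidence intervals for EAIRs.
- State that 'last visit' means the previous C-SSRS assessment.
- Keep the by-visit percentages, with the nominal look-back (4, 8, 12, 12, 16 weeks) in the column header.
- Treat any per-interval rate as supportive only, and restrict it to new-onset Yes answers. Dividing every Yes by its look-back would reverse the problem: if the same persistent cases answered Yes at each visit, the apparent rate would fall 4-fold from Week 4 to Week 52 (112/28), a falsely reassuring trend.

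The cost is SAP wording and one extra table from data and dates already collected, with no change to trial conduct. The rates will be imprecise because events are few, and the confidence intervals will show this.
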